13.4.2.1.2. Clinical Laboratory Tests

Change from Baseline will be summarized descriptively for each analyte.

The percentage of subjects with treatment-emergent ALT, AST, or alkaline phosphatase $>3 \times$ ULN and total bilirubin >2.0 mg/dL at the same evaluation will be summarized by treatment group.

Clinical laboratory results considered clinically important by the Investigator will be identified. Individual results for clinical laboratory tests (serum chemistry, hematology, and urinalysis) outside the normal range will be flagged in the data listings. Criteria to identify potentially clinically significant values will be defined in the Statistical Analysis plan.

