7.2. Study Endpoints

7.2.1. Safety Endpoints

The following safety endpoints will be assessed:

- Number and percent of subjects reporting treatment-emergent adverse events (TEAEs) by system organ class and preferred term.
- Number and percent of subjects reporting treatment-emergent serious adverse events (SAEs) by system organ class and preferred term.
- Number and percent of subjects reporting TEAEs resulting in study drug discontinuation by system organ class and preferred term.
- Change in vital signs from Baseline to each scheduled evaluation.

- Change in clinical laboratory values from Baseline to each scheduled evaluation.
- Percentage of subjects with treatment-emergent alanine aminotransferase (ALT), aspartate aminotransferase (AST), or alkaline phosphatase >3 × the upper limit of normal (ULN) and total bilirubin >2.0 mg/dL at the same evaluation.
- Percentage of subjects identified as suicide risk with Columbia-Suicide Severity Rating Scale (C-SSRS).

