8.6. Early Discontinuation Visit

If a subject is discontinued from the study before completion, regardless of whether they have received study drug, the reason for discontinuation must be documented in the subject's source document and eCRF. Whenever a subject is discontinued, the procedures/assessments listed for the EOS Visit in the Schedule of Assessments (Table 2 or Table 3) should be performed. If a subject discontinues on a scheduled visit, assessments completed at that visit should be entered into the eCRF for that scheduled visit. Assessments required for the EOS Visit that are not required at the scheduled visit (eg, a complete physical examination, clinical laboratory tests) should be completed and entered into the eCRF for the EOS Visit.

Subjects who prematurely discontinue the study will be instructed to taper study drug as described in Section 9.2.3 and to complete the at-home assessments for the study drug taper period (Table 4 or Table 5). Once discontinued, subjects may not re-enter the study.

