12. ASSESSMENTS OF SAFETY

Safety assessments will be performed at the time points outlined in Table 2, Table 3 and Table 4.

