12.1.7. Laboratory Assessments

See Table 10 for the list of clinical laboratory tests to be performed. Additional tests may be performed at any time during the study as determined necessary by the Investigator or required by local regulations. All study-required laboratory assessments will be performed by a central laboratory.

The Investigator must review the laboratory report and document this review. The laboratory reports must be filed with the source documents. Clinically relevant changes during the study that result in changes in study drug, study participation, or concomitant treatment use will be recorded as AEs on the eCRF. Clinically significant abnormal laboratory findings are those which are not associated with the underlying disease, unless judged by the Investigator to be more severe than expected for the subject's condition.

All laboratory tests with values considered clinically significantly abnormal during participation in the study should be repeated until the values return to normal or baseline or are no longer considered clinically significant by the Investigator or medical monitor. If such values do not return to normal/baseline within a period of time judged reasonable by the Investigator, the etiology should be identified, and the Sponsor notified.

All testing for opioids in the urine is qualitative, including confirmatory testing. Qualitative results will be reported for opioids by class with dipstick tests and by opioid analyte for urine specimens sent to the Sponsor's central laboratory. No quantitative testing for opioids will be performed or reported throughout the study.

All protocol-required laboratory assessments must be conducted in accordance with the laboratory manual.

Hematology ^a	Chemistry ^b	Urinalysis
Hemoglobin	Cholesterol	Color
Hematocrit	Triglycerides	Clarity
Red blood cells	Sodium	pН
Mean corpuscular volume	Potassium	Specific gravity
Mean corpuscular hemoglobin	Chloride	Protein
Mean corpuscular hemoglobin concentration	Carbon dioxide	Glucose
Red blood cell distribution width	Glucose	Ketones
White blood cell count	Creatinine	Bilirubin
Neutrophils	Albumin	Nitrite
Lymphocytes	Total protein	Blood
Monocytes	Calcium	Urobilinogen
Eosinophils	Phosphorus	White blood cell count
Basophils	Aspartate aminotransferase	Red blood cell count
Platelet count	Alanine aminotransferase	Epithelial cells
Prothrombin time	Gamma-glutamyl transpeptidase	Bacteria
Activated partial thromboplastin time	Total bilirubin	Casts

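### Change from Baseline is planned for every laboratory analyte, but hematology and urinalysis are scheduled at Screening only; and completers have no scheduled on-treatment liver test after Visit 4

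*Combined protocol and SAP*

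**What the plan says.** Laboratory assessments are among the tools for the primary safety objective (Section 6.4, Table 7). Section 7.2.1 lists as an endpoint: "Change in clinical laboratory values from Baseline to each scheduled evaluation". Section 13.4.2.1.2 gives the analysis: "Change from Baseline will be summarized descriptively for each analyte". The same section shows that all three panels are meant: "Individual results for clinical laboratory tests (serum chemistry, hematology, and urinalysis) outside the normal range will be flagged in the data listings".

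Timing is set elsewhere. Section 12 says: "Safety assessments will be performed at the time points outlined in Table 2, Table 3 and Table 4". In both Table 2 and Table 3, hematology and urinalysis carry one mark each, at Screening. Clinical chemistry carries three: Screening, Visit 4 and EOS. Visit 5 (both tables) and Visit 4P (Table 3) carry no laboratory panel. Section 12.1.7 points to Table 10 for the tests themselves and gives no visit times.

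For early discontinuation, Section 8.6 says that "the procedures/assessments listed for the EOS Visit in the Schedule of Assessments (Table 2 or Table 3) should be performed". It then refers to "Assessments required for the EOS Visit that are not required at the scheduled visit (eg, a complete physical examination, clinical laboratory tests". The EOS column has chemistry and a brief physical examination; the complete examination is marked at Screening only.

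The rationale in the Synopsis names hepatotoxicity among the signals that the trial must look for, because most existing safety data cover less than 14 days of use.

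**The concern.** There are two separate matters.

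1. An analysis is promised for data that the schedule does not collect. For hematology and urinalysis the change-from-Baseline tables would be empty, or filled only with results that an investigator happened to order. The latter would give no systematic comparison between arms.

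2. The trial is justified partly by liver safety beyond 14 days, yet a completer's only scheduled on-drug liver sample falls on Day 14, 15 or 16. An elevation that begins after Visit 4 and resolves before EOS would be missed by scheduled testing. The gap is longer for paused subjects, who have the longest exposure.

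**Working it through.** **Panels against the schedule.** Table 10 lists 16 hematology, 21 chemistry and 18 urinalysis items: 16 + 21 + 18 = 55. Items without a scheduled post-baseline value: 16 + 18 = 34, and 34/55 = 62%. Some urinalysis items, such as color and clarity, are categories for which a numeric change has little meaning; hematology alone is 16/55 = 29%. The single marks are not an extraction fault: in the same tables the chemistry row shows three marks, the COWS marks fall on the clinic visits, and Tables 2 and 3 agree.

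**Dosing days, checked against the plan's own figure.** Section 9.2.3 continues study drug for 5 days after the last opioid dose and then tapers it over 4 days.
- Standard: opioid dose zero from Day 13, so last opioid day 12; 12 + 5 + 4 = Day 21.
- Paused: opioid dose zero from Day 19, so last opioid day 18; 18 + 5 + 4 = Day 27.

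This reproduces the 21 to 27 days in Section 7.4. EOS minus last dose is 28 − 21 = 7 and 34 − 27 = 7 days.

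**Dosing days after the last scheduled on-drug liver test (Visit 4, Day 15).**
- Standard: 21 − 15 = 6 of 21 (5 to 7 over the ±1 day window).
- Paused: 27 − 15 = 12 of 27 (11 to 13).

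In both cases these days include the whole 4-day study-drug taper.

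**Longest interval between chemistry samples from Visit 4 to EOS, nominal days.**
- Standard: 28 − 15 = 13. With Visit 5 (Day 22): max(22 − 15, 28 − 22) = 7.
- Paused: 34 − 15 = 19. With Visit 5 (Day 28) only: max(28 − 15, 34 − 28) = 13. With Visits 4P (Day 21) and 5: max(21 − 15, 28 − 21, 34 − 28) = 7.

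With every visit moved within ±1 day, the present gaps are 11–15 (standard) and 17–21 (paused); with the added samples, 6–9 on both schedules.

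**Share of elevations that a scheduled sample would meet.** The documents give no duration, so this is an illustration under stated assumptions: onset is equally likely on each day from Day 2 to the last dose (20 or 26 days), the elevation lasts d days including the onset day, and it is caught if a draw falls within it. For d = 7 on the standard schedule, Day 15 catches onsets on Days 9–15 (7 of 20) and Day 28 catches none. Adding Day 22 catches onsets on Days 16–21, a further 6, giving 13 of 20. In the same way:

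| Schedule | d = 3 | d = 7 | d = 14 |
|---|---|---|---|
| Standard, now | 3/20 = 15% | 7/20 = 35% | 20/20 = 100% |
| Standard, with Visit 5 | 5/20 = 25% | 13/20 = 65% | 20/20 = 100% |
| Paused, now | 3/26 = 12% | 7/26 = 27% | 21/26 = 81% |
| Paused, with Visits 4P and 5 | 8/26 = 31% | 19/26 = 73% | 26/26 = 100% |

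Over all ±1 day windows the d = 7 shares are 35–40% (standard) and 27–31% (paused) now, and 60–70% and 62–77% with the added samples.

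**The case against.** On the first part, Section 13.1 calls the statistics section an overview, with details left to a later analysis plan. Section 7.2.1 speaks only of scheduled evaluations, so a panel with none might simply produce no table. Section 12.1.7 also allows extra testing: "Additional tests may be performed at any time during the study as determined necessary by the Investigator". No conclusion is biased, and the combined liver-enzyme and bilirubin endpoint needs chemistry only. The last two statements are correct and limit the harm. The others do not remove the conflict: Section 13.4.2.1.2 makes no exception for any panel, a later plan cannot create data that were not collected, and discretionary tests are not a scheduled comparison.

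Three stronger readings are tempting, and the documents do not support them.

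- A reader might infer that exposure beyond about Day 15 is not sampled at all. EOS chemistry follows the whole exposure and can show an elevation that persists for about a week. Subjects who discontinue early have the EOS assessments, including chemistry, at discontinuation. What is missing is a scheduled on-treatment test after Visit 4 in completers.
- A reader might infer that chemistry at Visit 5 supplies a second on-drug sample. On the standard schedule Visit 5 is nominally one day after the last dose, so the count of 6 of 21 days does not change. Only Visit 4P, in paused subjects, is nominally on drug, and the documents give no expected pause rate.
- A reader might infer that Section 8.6 requires all of Table 10 at early discontinuation, so that hematology and urinalysis would exist only in early discontinuers. Section 8.6 first refers to the EOS column, which contains chemistry, and its mention of laboratory tests fits that. Only the complete physical examination conflicts with the tables.

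Against the second part it is fair to say that no section promises more frequent liver testing, that this is a pilot, and that adverse events are collected throughout. The illustration concerns any elevation, not the joint enzyme and bilirubin event, and its gain comes from the shorter assumed durations. All of this stands, which is why the second part is offered only as an improvement.

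**Conclusion.** The first part holds and rests on no assumption: 34 of the 55 Table 10 items have no scheduled post-baseline value, so the analysis in Section 13.4.2.1.2 cannot be carried out for hematology or urinalysis from scheduled data. The calculation of the liver endpoint is not affected.

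The second part holds as a cheap improvement. At nominal days, completers have no scheduled on-treatment liver test in the last 6 of 21 dosing days (12 of 27 if paused), and 13 or 19 days pass between chemistry samples. How much extra sampling would find depends on assumed durations and uniform onset. For 14-day elevations there is no gain at nominal days on the standard schedule; for 7-day elevations the gain is 30 percentage points (standard) and 46 (paused, 12/26). More samples do not relax the limit set by sample size: for 0 events in 30 subjects the exact two-sided 95% upper limit is 1 − 0.025^(1/30) = 11.6% under any schedule. The benefit is a shorter unobserved interval in the exposure period that the rationale singles out.

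**What to change.** **Part 1, correction.** Choose one of two routes and make Sections 7.2.1 and 13.4.2.1.2 agree with Tables 2 and 3.
- Restrict the change-from-Baseline endpoint and analysis to chemistry. This is wording only.
- Or add hematology and urinalysis at Visit 4 and EOS, where blood and urine are already collected: at most 60 × 2 = 120 tests of each panel.

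Also reconcile the complete physical examination in Section 8.6 with the brief one in the EOS column.

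**Part 2, optional improvement.** Add the existing chemistry panel at Visit 5 in Tables 2 and 3 (an end-of-exposure sample) and at Visit 4P in Table 3 (Day 21, on drug). In paused subjects this reduces the dosing days after the last on-drug test from 12 to 27 − 21 = 6. The cost is at most 60 panels at Visit 5 plus one per paused subject at Visit 4P, so 60 to 120 in all. The downside is one extra blood sample per subject, or two if paused. Section 12.1.7.1 ties the ethyl glucuronide result to Visit 4 and would need a matching edit.

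Both parts fit in one amendment to two tables and a few sentences. They need no new visit and change no dose, dosing schedule or stopping rule.

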13.4.2.1.3. Electrocardiogram

The interpretation of electrocardiogram and interval duration measurements by the designated electrocardiogram laboratory cardiologists will be reviewed by the Investigator. Clinically significant deteriorations from Baseline will be reported and summarized as TEAEs.

13.4.2.1.4. Vital Signs

Change from Baseline to each scheduled measurement will be summarized descriptively. Criteria to identify potentially clinically significant values will be defined in the Statistical Analysis plan.

13.5. Interim Analysis

A Data Monitoring Committee (DMC) will be established to review safety and efficacy data in an unblinded manner. The DMC will consist of, at a minimum, 3 subject matter experts including a pain physician, psychiatrist/psychologist, and a statistician. A formal charter will be developed and signed prior to the unblinded interim analysis. The charter will address the review of safety data including AEs (eg, incidence of drop-outs due to AEs or intolerable opioid withdrawal, suicidality, cardiovascular events, urine drug screen results, alcohol test results, other laboratory results, etc) and stopping rules that will render the study unfeasible to continue (eg, a lack of measurable opioid withdrawal symptoms).

The interim analysis will be conducted after approximately 30 subjects have completed or discontinued the study. There will be no formal statistical analysis for futility; however, the study may be stopped for futility, but it will not be stopped for a positive demonstration of effectiveness, providing the DMC determines the risk-benefit ratio is acceptable. Therefore, no adjustment of Type I error is necessary.

14. SUPPORTING DOCUMENTATION AND OPERATIONAL CONSIDERATIONS

14.1. Regulatory and Ethical Considerations

This study will be conducted in accordance with the protocol and with the following:

- Applicable International Council for Harmonisation (ICH) and Good Clinical Practice (GCP) guidelines
- US Code of Federal Regulations (CFRs) dealing with Protection of Human Subjects (21 CFR Part 50), Financial Disclosure (21 CFR Part 54), IRBs (21 CFR Part 56) and Investigational New Drugs (21 CFR Part 312)
- the Nuremberg Code
- the Declaration of Helsinki, revised version of Seoul, October 2008 (in compliance with FDA guidance)
- Applicable laws and regulations

The purpose of these regulations, legal obligations, and guidelines is to define the standards and principles for the proper conduct of clinical trials that have been developed by the medical, scientific, and regulatory communities. They are not intended to impede or restrict clinical research. Copies of these materials can be downloaded from the FDA website at www.fda.gov.

The protocol, protocol amendments, informed consent form (ICF), package insert for LUCEMYRA [USWM 2018], and any other relevant documents must be submitted to an IRB/IEC by the Investigator and reviewed and approved by the IRB/IEC before the study is initiated.

The Investigator will be responsible for the following:

- Providing written summaries of the status of the study to the IRB/IEC annually or more frequently in accordance with the requirements, policies, and procedures established by the IRB/IEC
- Notifying the IRB/IEC of SAEs or other significant safety findings as required by IRB/IEC procedures
- Providing oversight of the conduct of the study at the site and adherence to requirements of 21 CFR, ICH guidelines, the IRB/IEC, European regulation 536/2014 for clinical studies (if applicable), and all other applicable local regulations

14.2. Informed Consent

Properly executed informed consent, in compliance with 21 CFR 50, ICH guidelines, and regional/local regulations, shall be obtained from each subject before entering the subject into the study. Attention is directed to the basic elements that are required in the informed consent under US CFR for Protection of Human Subjects (21 CFR 50.25) and/or ICH E6 4.8.10. Where applicable, the consent form or appended document must also include required elements to maintain compliance with 45 CFR Part 164 (Heath Insurance Portability and Accountability Act) and/or 21 CFR Part 50.27/ICH E6 4.8.8.

Informed consent is a process of interaction between the Investigator and a potential subject in which the Investigator (or appropriate designee) explains the aims, methods, anticipated benefits (or lack thereof), and potential risks of participating in a study, and informs the potential subject of their rights. The subject will be given ample time and opportunity to inquire about details of the study so the subject can voluntarily make an informed decision about whether or not to participate in the study. All potential subjects will be given a current IRB- and Sponsor-approved copy of the ICF to read to ensure they are given accurate information, and to assist in verifying that consent was obtained. Information provided verbally, as supplemental explanation and/or answers to questions, must be accurate and consistent with the ICF, and must not be coercive or misleading. No subject will undergo any study procedures before the subject signs and dates the ICF, which should be signed before Screening. A completed, signed copy will be given to the subject and a signed original shall be maintained in the subject's clinical file. Subjects who refuse to participate or who withdraw from the study will be treated without prejudice.

Potential subjects are to be consented using an ICF that is written in a language they understand. If the person obtaining consent is not fluent in the language in which the consent is written (ie, is not able to explain the consent/answer questions to the subject), the subject's consent must be witnessed by someone who is fluent in the language in which the consent is written, and must have the ability to translate any questions/explanations during the consent process.

Each subject must also sign a Health Insurance Portability and Accountability Act authorization form before his/her participation in the study. A signed copy must be provided to the subject and a signed original shall be maintained in the subject's clinical file.

14.3. Source Documents and Retention

Source documents provide evidence for the existence of the subject and substantiate the integrity of the data collected. Information recorded on source documents are to be attributable, legible, contemporaneous, original and accurate and allow reconstruction of the trial from start to finish. It is the responsibility of the Investigator to ensure that source documents capture all required information needed for the verification of data required by the protocol and that data captured on the eCRF match information recorded in source. The Investigator may need to request previous medical records from the subject's primary care or other relevant physician. There may be instances where eCRF data are considered source data. These include the following assessments:

- Subject completed questionnaires (electronic patient reported outcome)
- Opioid Use Characterization
- Characterization of Opioid Withdrawal History
- Characterization of Pain Condition

Source documents and site study records including signed informed consent forms are to be maintained on site during the duration of the study and retained by the Investigator for 2 years after study completion unless local regulations or institutional policies require a longer retention period. No records may be destroyed during the retention period without the written approval of the Sponsor. No records may be transferred to another location or party without written notification to the Sponsor.

14.4. Subject Confidentiality

Subject confidentiality and privacy will be strictly held in trust by the participating Investigators, their staff, and the Sponsor(s) and authorized representatives of the Sponsor. Therefore, the study protocol, documentation, data, and all other information generated will be held in strict confidence. No information concerning the study or the data will be released to any unauthorized third party without prior written approval of the Sponsor.

The study monitor, other authorized representatives of the Sponsor, representatives of the IRB, regulatory agencies or the pharmaceutical company supplying study product may inspect all documents and records required to be maintained by the Investigator, including but not limited to, medical records (office, clinic, or hospital) and pharmacy records for the subjects in this study. The clinical study site will permit access to such records.

Subjects will be assigned a unique identifier by the site. Any subject record or dataset that is transferred to the Sponsor or authorized representative of the Sponsor will contain the identifier only; subject names or any information which would make the subject identifiable will not be transferred.

The study data entry and study management systems used by clinical sites and by research staff will be secured and password protected. At the end of the study, all study databases will be de-identified and archived.

Subject confidentiality will be maintained in any publications or presentations that result from this study

